#### **Participants, sampling method, sample size, and setting**

Participants in the study will be SCI inpatients from the Gaza Strip, both genders, of any cause or type of SCI, and age 18-65 years. They will be recruited from admitted inpatients in one of the three rehabilitation settings (Hamad, ElWafa, or ElAmal Rehabilitation hospitals). Readmissions will be included in the study if they are eligible. These three inpatient rehabilitation hospitals are located in the Gaza Strip of Palestine and are private sector health services. They provide comprehensive rehabilitation services. Their rehabilitation teams include physical rehabilitation doctors, rehabilitation nurses, physiotherapists, occupational

therapists, speech therapists, clinical dietitians, psychologists, social workers, orthoptists, and community-based rehabilitation workers. The sample size was determined to detect an effect size of 15%, power of 80%, 5% margin of error, and 95% Confidence Interval (CI). The study sample of 90 SCI individuals will be randomized to two groups, conventional therapy (n1=45) and intervention/SADL-eM & conventional therapy (n2=45) using a simple randomization approach. Inclusion and exclusion criteria are listed in Box 1.

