The purpose of the SADL-eM is to serve as a treatment tool during inpatient rehabilitation. Over the first week of admission of each person with SCI in each facility, a research clinical supervisor will recruit study participants based on the study eligibility criteria, obtain consent, and assign each consenting patient to one of the two study groups. They will then provide each participant in the intervention group with a SADL-eM hard copy, and explain the purpose of the manual and how to use it. The manual will be reviewed by the treating occupational therapist and the person with SCI during their treatment sessions. During occupational therapy sessions, the therapist will refer to the relevant chapter of the manual. The therapist will also indicate to the participants which parts of the manual are not relevant to them (based on their gender, driving status, or level of SCI). Participants' queries on the content of the manual will be answered by the treating occupational therapist. The therapist will include the manual in as many SADL-eM educational sessions as required, but not less than three sessions per week with 15 minutes per session. The minimum level of clinical experience of each treating occupational therapist will be two years. Good Arabic language comprehension, and the ability to read and write is mandatory for both therapists and patients. No other special skills or experience are required.

The participants will keep the manual to review after sessions and after discharge from the inpatient rehabilitation setting. For the purposes of the study, blinding and bias reduction, the therapists and the participants in the intervention group must not share any part of the manual or information included with other patients or staff. The research assistant who performs data collection, the clinical supervisor, and occupational therapy team will be invited for informational session prior to data collection in each of the participating settings. The informational session will focus on the study purpose, recruitment, eligibility criteria, use of

the SADL-eM, roles, bias reduction, and blinding. Use of data collection tools will take place in a separate session with the research assistant. The principal researcher will answer all questions of the research team during informational sessions and during the research.

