For the purposes of the current study, the SADL-eM will be provided during face-to-face individual occupational therapy sessions without any constraints regarding treatment area. It could be occupational therapy department, patient ward, and educational activities room. The face-to-face manual delivery does not require any infrastructure or special equipment.

The number of sessions, time allocated, and frequency are determined by each therapist and participant. Determinants may include participant's capabilities, potentials, and progress during treatment; and the scope of the service such as time allocated for each patient, therapist-patient ratio, and frequency of inpatient sessions. The therapist and the participant will continue to use the manual during treatment sessions until they decide there is no need for further use of the manual or the participant is discharged. Treating occupational therapists will retain records of any change or modification of the SADL-eM administration. The researchers will conduct a pilot study in a similar sample of 15 S people with SaCIs to improve the use of intervention and data collection tools.

Nonadherence to medical treatment in clinical trials of medical efficacy has serious consequences on the quality of research. It may obscure data collected and disrupt findings obtained (Quittner, et al., 2000). The steps to ensure adherence to the intervention during study include clearly defining the intervention, measuring, and then comprehensively reporting adherence to the intervention. Attendance records collected by the therapist (times, duration, and intensity of treatment; manual elements covered) and SADL-eM adherence therapist-report questionnaire will be used to measure and report adherence to the SADL-eM intervention. The manual will be made freely available on the Stellenbosch University website when the research is complete.

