## **Data Collection**

All admitted SCI patients will be evaluated by the research supervisor in the setting for eligibility within three days of admission to the inpatient rehabilitation setting, until the desired sample size is reached. Eligible individuals will sign a consent form and then be assigned randomly to one arm of the study by the research supervisor. The allocation sequence will be concealed from patients, therapist and, assessor. The data about exposure to the educational intervention will be collected by a separate research assistant by phone and will be concealed

from the assessor. Each occupational therapy department will assign four therapists to follow up the trial cases – two for the intervention and two for control group. All the staff in the occupational therapy department, participants, and assessors will be requested not to discuss the trial and intervention material between them. The importance of concealing any information until the end of the study will be explained. Study participants are not allowed to switch between occupational therapists or study arms. They will be asked not to participate in other educational interventions (peer or external) related to their rehabilitation or seek treatment outside their trial. The head of occupational therapy department within each rehabilitation setting will supervise participants and assigned occupational therapists in both study arms to reduce contamination bias such as sharing intervention content with the control group, sharing similar time and space of occupational therapy sessions, and exchange of therapists.

Contamination bias due to already existing background and/or receipt of additional educational interventions will be measured within each arm of the study (Chi-Square test to compare the progress means). However, no case will be eliminated from statistical analysis due to contamination bias.

The study will adopt approaches to prevent loss of participants to follow-up by making questionnaires as easy to complete as possible, providing incentives in the form of a free copy of the educational manual for the control group, and explaining the importance of the study (Magill, et al., 2019).

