## **Data Analysis**

Captured data will be coded and reviewed by the researchers for clarity and completion. A spread sheet will be prepared by the three researchers and then loaded to IBMSPSS 21 for analysis. The first author will perform data entry. The research assistant will check the data entry using the original forms, and the research supervisor will check the data for missing data and entry errors.

The following statistical methods will be used to test the research hypothesis:

- a. To describe participants' characteristics: descriptive statistics such as frequency, percentage, mean with standard deviation for Normally distributed data and median and Inter Quartile range will be used for continuous variables that are not Normally distributed will be used.
- b. Missing values will not be substituted. Intention-to treat analysis method will be used for analysis.
- c. To determine the significance of biographical variables at baseline: McNemar and Chi Square with Nominal variables, T-test and Mann-Whitney for interval variables will be used.
- d. To compare the efficacy of the educational manual: Repeated Measures ANOVA/ Linear Mixed Models will be used will be used to assess differences between intervention and control group using the ADL data. The Repeated Measures ANOVA and Linear Mixed Models will be used to analyze the data. Linear Mixed Models has advantage in dealing with missing values and provides fixed and random effect (Krueger and Tian, 2004).
- e. Adherence to the intervention will be summarized using frequency and percentage.

All the data collected and entered (hardcopy and soft copy) will be securely stored by the first researcher in a locked cabinet on hospital premises (hardcopy) and in a password-protected file online.

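### Departments decide which therapists treat which arm, with no random or balanced split, so therapist is fully confounded with the SADL-eM effect

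*Combined protocol and SAP*

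**What the plan says.** Only patients are randomised. Under Data Collection: "Eligible individuals will sign a consent form and then be assigned randomly to one arm of the study by the research supervisor". The random number table at the end of the document draws 46 numbers from a range of 1 to 92, which can only be a list of patients.

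Therapists reach their arms by another route. The same section says "Each occupational therapy department will assign four therapists to follow up the trial cases", split as "two for the intervention and two for control group". It adds: "Study participants are not allowed to switch between occupational therapists or study arms". The head of each department is to supervise against exchange of therapists. Patients come from "one of the three rehabilitation settings".

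The stated requirements for therapists are minimum standards. In the SADL-eM section: "The minimum level of clinical experience of each treating occupational therapist will be two years". Beyond that, only language ability is asked for. The same section leaves delivery partly to the therapist, above a stated weekly minimum: "The number of sessions, time allocated, and frequency are determined by each therapist and participant".

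Data Analysis says "The Repeated Measures ANOVA and Linear Mixed Models will be used to analyze the data". It mentions fixed and random effects as a general advantage of mixed models, but names no term for therapist or hospital.

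**The concern.** Both arms receive usual care, and the occupational therapy part of that care comes from the therapist assigned to the arm. The trial therefore compares the manual delivered by one set of therapists with usual care delivered by another set. Randomising patients balances the patients and does nothing to balance the therapists.

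The departments make the split knowing what each pair will do. A minimum of two years' experience does not make the pairs alike. If the pairs differ in their effect on SCIM-SR or SCIM-III, that difference is added to or subtracted from the manual's effect. The data cannot separate the two, because no therapist treats both arms. The blinded assessor does not help, since the difference would lie in the care given and not in its assessment.

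This is distinct from clustering. A therapist random effect widens the interval to reflect variation between therapists. It does not move an estimate that has been shifted by who was chosen.

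**Working it through.** **Structure.** 3 hospitals × 4 therapists = 12 therapists, 6 per arm. With 45 patients per arm, that is 45/6 = 7.5 patients per therapist on average.

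**The plan's own figure.** The sample-size paragraph gives 90 patients, 80% power and an effect size of 15%, without saying what the 15% measures. N = 90 is reproduced if 15% is read as Cohen's f = 0.15 for the group-by-time interaction, with an assumed correlation of 0.5 between the two time points. Then λ = f²·N·m/(1−ρ) = 0.0225 × 90 × 2/0.5 = 8.1, and power on 1 and 88 df is 80.4%. The equivalent standardised difference between arms in change is √(2 × 8.1/45) = 0.60 SD. This calculation treats patients as independent of therapist.

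**Worst-case selection.** The documents give no therapist ICC, so 2%, 5% and 10% are assumed. They apply to whichever outcome is analysed.

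- The expected values of four ordered standard normal values are ±1.029 and ±0.297.
- Mean of top two minus mean of bottom two = (1.029 + 0.297)/2 × 2 = 1.326 therapist SDs.
- In outcome SDs, multiply by √ICC: 1.326 × 0.141 = 0.19; 1.326 × 0.224 = 0.30; 1.326 × 0.316 = 0.42.

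This needs perfect ranking in all three departments and the same favoured arm in each. With equal numbers of patients per hospital, if two departments favoured one arm and the third the other, the net shift would be (2 − 1)/3 of these values: 0.06, 0.10 and 0.14.

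**What a shift would do.** With no manual effect and a simple two-sided 5% test, the standard error is √(2/45) = 0.211 SD. A shift of 0.2, 0.3 or 0.4 SD gives a significant result with probability of about 16%, 30% or 47.5%.

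**What a draw by lot leaves.** The expected shift is zero, but 6 against 6 therapists still differ by chance, with SD √(2/6) = 0.58 therapist SDs. In outcome SDs that is 0.08, 0.13 and 0.18 at the same ICCs. An analysis that ignores therapist does not count this variation. The design effect is 1 + (7.5 − 1) × ICC, and the true error of the unadjusted test is 2 × [1 − Φ(1.96/√DE)].

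| Assumed ICC | Design effect | True two-sided error, therapist ignored | Power at N = 90, 88 df | Power at N = 90, 10 df |
|---|---|---|---|---|
| 2% | 1.13 | 6.5% | 75% | 68% |
| 5% | 1.325 | 8.9% | 69% | 61% |
| 10% | 1.65 | 12.7% | 59% | 52% |

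The 10 df are 12 therapists minus 2 arms. A fixed hospital term would leave 8.

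**The case against.** **Separate therapists are deliberate.** They keep the manual's content away from controls, and the plan has the department head police this. That stands: the separation should remain, and nesting alone is not the defect.

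**Silence is not preference.** A reader might infer that departments will give the manual to their keenest or most experienced staff, so that its effect will be overstated. Nothing in the documents says so. Senior staff might equally be kept on usual care, which would bias against the manual. A reader might also infer that the split is made after staff have been shown the manual. The plan places the informational session before data collection, but does not say whether therapists are assigned before or after it. The point needs neither inference.

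**The sizes are a ceiling.** They rest on perfect ranking, agreement between hospitals and assumed ICCs. Each hospital's team also includes nurses, physiotherapists, doctors and others who are not assigned by arm, so the occupational therapist's share of outcome variance could be small. This stands.

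**Lots are not a full cure.** Chance imbalance among 12 therapists remains, and still no therapist treats both arms. This also stands, and is why the model needs a therapist term as well. Lots do remove the part that no analysis can repair: a shift due to choice.

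**Conclusion.** The concern holds as a matter of design. Therapist is completely confounded with arm through a split left to each department, with no random or balanced method stated and nothing in the analysis to address it. It should be changed before recruitment.

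The documents do not support saying that the comparison is biased, or in which direction. They show only that any difference produced by the choice would be attributed to the manual. As a worst case that is 0.19 to 0.42 outcome SDs at assumed ICCs of 2% to 10%. This compares with the 0.60 SD that the sample size appears built to detect, if f = 0.15 and a correlation of 0.5 are the right reading. With weaker or conflicting preferences the shift would be smaller, and it could be nil.

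**What to change.** 1. In Data Collection, state that each department first names its four therapists. They are then allocated two and two to the arms by lot before the first patient is enrolled, with the draw made by someone outside the department. Pairing the four on years of experience and drawing within pairs is an optional refinement.
2. Record each therapist's experience and report it by arm.
3. In Data Analysis, specify hospital and a therapist random effect in the linear mixed model, with small-sample degrees of freedom (for example Satterthwaite).
4. Keep the separation of therapists and the supervision against exchange. State as a limitation that no therapist treats both arms.

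If therapists have already been assigned by choice, items 2 to 4 still apply, but they cannot remove a shift due to selection.

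The cost is one draw per hospital and a few sentences, with no extra staff or patients. The department gives up choosing who delivers the manual. The interval widens by a factor of √DE: about 6%, 15% or 28% at ICCs of 2%, 5% or 10%, and somewhat more with few degrees of freedom. That is slight if therapists differ little. If they differ more, it reflects uncertainty that the unadjusted analysis would hide.

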The researchers will use the same outcome measures all through the study and with both of study arms. Biographical data will be collected by a research assistant once on the participant's admission and consent to participate. ADL data collection from each participant in the study will take place in a face-to-face interview twice (on admission before providing with the educational manual and 6 weeks later) using: (a) Patient-administered SCIM-SR and (b) Research assistant-administered SCIM-III, the Private Religiousness Practices Scale, Organizational Religiousness Short-Form, and the domains of ADL covered by the educational manual including driving and community mobility, personal device care, health management and maintenance, Wudu, and Salat. The data will be used to compare the results and means of both groups, answer the research question, and test the study hypothesis.

Polit, et al. (2001) pointed out that the validity of the experimental study can be threatened by history, selection, and maturation. This study finding's validity will be enhanced by concealing intervention group using a blinded assessor. The bias of sampling and contamination will be

minimized through randomization and assuring freedom of participation and anonymity of participants.

Objective data collected in clinical settings using valid and reliable tools is essential for evaluating the impact of an intervention (Polit, et al., 2001). The validity and reliability of the data collected and results of the study will be improved using standardized measurement tools such as SCIM-III and SCIM-SR.

**Biographical Data Collection Tool:** an English 24-item tool that captures demographic and socioeconomic data including age, gender, marital status, level of education, employment, monthly income, accommodation, diagnosis, and cause and type of SCI. The researchers developed the tool to be used in English version in this study.

**Spinal Cord Independence Measure-Self Reported (SCIM-SR):** a patient-reported 17-item tool that evaluates the ability of a person with SCI to perform specified activities independently, with assistance, or with assistive devices. The tool uses an ordinal scale.

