Research supports the criterion validity of SCIM-SR as compared with SCIM III. Pearson correlation and ICC coefficients of the total and the subscale scores met the quality criterion of being above 0.7. The tool is not available in Arabic (Fekete, et al., 2013). The first author will translate the SCIM-SR to Arabic. The Arabic translation will be piloted in the pilot study.

**Spinal Cord Independence Measure-III (SCIM-III):** a 17-task tool that evaluates the ability of a person with SCI to perform specified activities independently, with assistance, or with assistive devices. It is therapist-reported and requires 30 to 45 minutes to complete by assessment but, the interview requires less time [about 20 minutes] (Fekete, et al., 2013). The SCIM has been evaluated in multiple countries including the Middle East and it appears to be resistant to cross-cultural differences. The SCIM-III is valid for use in clinical practice to evaluate function and plan goals of rehabilitation (Glass, et al., 2009). The tool uses an ordinal scale with total score range between 0-100. A higher score indicates greater ADL performance. The SCIM-III has good reliability: Cronbach's alpha: 0.70-0.78, Kappa co-

efficient: 0.64-0.84. Pearson correlation and ICC coefficients of the total and the subscale scores met the quality criterion of being 0.84-0.94. The tool is not available in Arabic and will be used in its English version (Anderson, et al., 2008). Good English language comprehension, and the ability to read and write is mandatory for therapists.

**The Private Religious Practices Scale:** a 4-item tool that measures the frequency of individual's involvement in religious behaviours: prayer, religious attendance (attending a church or mosque), reading the Bible/Quran, and watching religious programs on television (Fetzer Institute, 2003). The tool uses an ordinal scale and it has acceptable reliability ( $\alpha=0.70$ ). It can be therapist-reported or patient-reported. The tool is not available in Arabic and will be used in its English version (Bodling, et al., 2013).

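### The contamination check names a chi-square test to compare mean progress, which that test cannot do; McNemar in Data Analysis item c has no paired data to work on (both minor)

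*Combined protocol and SAP*

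**What the plan says.** The Data Collection section names what is to be examined, "Contamination bias due to already existing background and/or receipt of additional educational interventions", and says that it "will be measured within each arm of the study (Chi-Square test to compare the progress means"). The same section gives a data source: "The data about exposure to the educational intervention will be collected by a separate research assistant by phone". It also limits the use of the result: "no case will be eliminated from statistical analysis due to contamination bias".

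For the outcome scale, the SCIM-III description states: "The tool uses an ordinal scale with total score range between 0-100". Both SCIM instruments are assessed on admission and six weeks later, so progress is a change in score.

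The Data Analysis section does not mention the contamination check. Its item c, on biographical variables at baseline, lists McNemar and chi-square for nominal variables, and the t-test and Mann-Whitney for interval variables. On the timing of those variables, Data Collection says: "Biographical data will be collected by a research assistant once on the" participant's admission. Study Design describes a parallel two-arm trial.

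**The concern.** The test and the quantity do not match. A chi-square test of association asks whether the frequencies in a table depend on group; it does not compare means. To use it here, the analyst would have to invent progress categories, substitute a rank test, or cross-tabulate raw change scores. The plan does not say which.

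The protocol takes contamination seriously. It separates the therapists by arm, has department heads supervise, and asks participants and staff not to share material. Since no patient is removed for contamination, this check is the only stated analysis of whether contamination was related to progress. A test that hardly ever rejects could be reported as evidence of no effect.

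Item c has a smaller fault of the same kind. McNemar needs paired nominal observations, and none exist for variables recorded once in two independent groups.

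**Working it through.** **Inputs from the documents.** 45 patients per arm (Participants, sampling method, sample size, and setting); SCIM-III total 0-100; comparison made within each arm.

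**Inputs assumed.** Number contaminated in an arm, k = 5 to 22; normal change scores rounded to whole points; SD of change 10 or 15 points. The documents give none of these.

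**1. The plan's own figure.** The contamination check has no stated figure. The only design figure is N = 90. It is reproduced by the group-by-time test with 2 groups and 2 time points, if the stated 15% is read as Cohen's f = 0.15 and the correlation is taken as 0.5 (both assumptions). The noncentrality is f² × N × 2/(1 − 0.5) = 0.0225 × 90 × 2/0.5 = 8.1 on 1 and 88 df, giving power 0.804; N = 88 gives 0.795. Nothing in this calculation involves the contamination check.

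**2. Limiting case of the literal test.** Suppose all 45 change scores differ and k = 10. Each column of the table then holds one patient.
- Expected counts per column are 10/45 = 0.222 and 35/45 = 0.778.
- A contaminated patient's column contributes (1 − 0.222)²/0.222 + 0.778²/0.778 = 2.722 + 0.778 = 3.5.
- Any other patient's column contributes 0.222 + (1 − 0.778)²/0.778 = 0.222 + 0.063 = 0.286.
- The total is 10 × 3.5 + 35 × 0.286 = 45 on 44 df, so p = 0.43.

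This holds whichever patients improved most, so the statistic carries no information about the means.

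**3. Realistic ties.** I simulated 4,000 arms per setting with a true difference of 1 SD. The 45 patients gave about 27 to 32 distinct change values on average, and more than 99.9% of expected counts were below 5.

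| SD, k | Literal chi-square rejects | t-test rejects |
|---|---|---|
| 15, k = 10 | 0.5% | 78% |
| 15, k = 15 | 0.2% | 87% |
| 10, k = 10 | 2.4% | 78% |
| 10, k = 15 | 0.8% | 87% |

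Exact noncentral-t power is 77.8% at k = 10 and 87.1% at k = 15, which agrees.

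**4. Precision of the replacement.** Half-width of the 95% interval in SD units = t(0.975, 43) × √(1/k + 1/(45 − k)), with t = 2.017.
- k = 5: 2.017 × 0.474 = 0.96
- k = 10: 2.017 × 0.359 = 0.72
- k = 15: 2.017 × 0.316 = 0.64
- k = 22: 2.017 × 0.298 = 0.60

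From k = 22 to k = 5 this is 6.0 to 9.6 points at an SD of 10, and 9.0 to 14.3 points at 15. All 45 are taken to have both assessments; missing values would widen the intervals.

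**5. McNemar.** One biographical record per participant and two independent arms give no within-person or matched pairs. The chi-square test listed beside it already handles the nominal comparison.

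**The case against.** The strongest reply is that this is loose wording in a supporting check. No decision depends on it, no case is removed, and a sensible analyst would not cross-tabulate raw scores. The instruments are called ordinal, so a rank test such as Kruskal-Wallis, which is referred to a chi-square distribution, may have been meant. At 1 SD that test detects 74-85% in the same simulated settings, so little would be lost. This is a fair argument for a low grade. It does not rescue the text: no rank test is named for this check, and a rank test does not compare means. Nor can the wording mean a comparison of contaminated proportions between arms, because it specifies progress and within each arm.

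A reader might also infer that contamination status is left wholly undefined. The documents do not support that: two sources are named and a phone route is given. What is absent is the coding. Readmission is allowed ("Readmissions will be included in the study if they are eligible"), but earlier rehabilitation plausibly falls under existing background.

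A further temptation is to say that prior education goes unrecorded, because the biographical tool "captures demographic and socioeconomic data including age, gender, marital status, level of education" and other items without mentioning it. That description is of a 24-item tool and lists only some of its contents, so the silence shows nothing.

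**Conclusion.** The point holds as a minor correction. The named test does not fit the stated comparison, and nothing elsewhere in the plan repairs it. The mismatch needs no assumptions. The size of the loss (0.2-2.4% detection against 78-87%) rests on the literal reading, the assumed SDs, 10 or 15 contaminated patients, and normal change scores. Deleting McNemar is right but changes little, because valid tests stand beside it.

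Three stronger conclusions should not be drawn. First, the main efficacy result is not compromised: the repeated measures or mixed-model comparison and N = 90 do not use this check. Second, no particular power loss from dichotomising progress can be charged to the plan. It defines no cut-point, and for a median split with 10 contaminated patients the detection rate at 1 SD moves from about 58% to 38% merely by adding a continuity correction. Third, secondary objective f is not shown to be wrongly analysed. Its outcome and model are not spelled out, but that is missing detail, and the mixed model in item d could carry those variables.

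**What to change.** 1. **Data Collection, contamination check.** Replace the chi-square test with the difference in mean SCIM-SR change from admission to six weeks, and likewise for SCIM-III, between patients with and without a recorded contamination source, within each arm, with a 95% confidence interval. Label it descriptive, because exposure to contamination is not randomised. Keep chi-square only for comparing proportions.
2. **Same paragraph.** State how the phone-collected exposure data are coded for each of the two named sources, existing background and additional education.
3. **Data Analysis, item c.** Delete McNemar; keep chi-square, the t-test and Mann-Whitney.

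The cost is wording in two sections. It needs no extra patients or visits and no change to the primary analysis. If the phone questions do not already separate the two sources, one or two yes/no items would be added. The drawback is imprecision: with half-widths of about 0.60 to 0.96 SD, an interval that includes zero will not rule out a sizeable difference, and the report should say so.
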